4.2. Inclusion criteria

Patient eligibility will be reviewed and documented by a suitable member of the investigator's study team before the patients are enrolled in the study.

Patients must meet all the following inclusion criteria to be enrolled in the study:

- Subject is an adult \geq 18 years at the time of informed consent and has signed informed consent before any trial related activities and according to local guidelines.
- Subject has histologically confirmed adenocarcinoma of the prostate without neuroendocrine differentiation or small cell features.
- Subject has bone metastases due to the prostate cancer and absence of visceral metastases.
- Subject has a serum testosterone of \leq 1.7 nmol/L (or \leq 50 ng/dL) at screening.
- Subject must have received a minimum of 24 weeks of treatment with abiraterone acetate or enzalutamide within its approved label indication and has discontinued use at least four weeks prior to start of study drug at day 1.
- Prior use of docetaxel is allowed in castration-naïve patients (maximum of six cycles).
- Subject receives and will continue to receive ongoing androgen deprivation with LHRH analogue therapy throughout the course of the study or has had a bilateral orchiectomy.
- Subject is asymptomatic from prostate cancer, defined as patients with the score on brief pain inventory (short form) (BPI-SF) Question #3 must zero and no use of opiate analgesics for prostate cancer-related pain currently or anytime within two weeks prior to screening.
- Subject has an Eastern Cooperative Oncology Group (ECOG) performance status of 0–1 at screening.
- Subject receiving bisphosphonate or other approved bone-targeting therapy must have been on stable doses for at least four weeks prior to start of study drug at day 1.
- Subject has a life expectancy of more than or equal to 12 months.
- Subject agrees not to participate in another interventional study while on study drug.
- Subject and his female partner who is of childbearing potential must use two acceptable methods of birth control (one of which must include a condom as a barrier method of contraception) starting at screening and continuing throughout the study period and for six months after final study drug administration.

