## **6. Analysis sets**

### Full analysis set

All patients that accomplish selection criteria and receive at least one dose of study medication.

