### **6.1 Protocol Deviations**

Protocol deviations will be recorded in the EXPERIOR database. A by-patient listing of protocol deviations and a by-patient listing of inclusion and exclusion criteria not met will be provided.

Major protocol deviations are defined as those deviations from the protocol likely to have an impact on the perceived efficacy and/or safety of study treatment.

To determine the per protocol set, all protocol deviations will be reviewed prior to database lock to determine which ones should be classified as major deviations. Patients with major protocol deviations will be excluded from the per protocol set.

Major protocol deviations may be discussed in the data review meeting. Criteria for determining full analysis set would be established by the Steering Committee (SC) before the statistical analysis begins.

Major protocol deviations and any action to be taken regarding the exclusion of subjects or affected data from specific analyses are defined below.

A summary of the number and percentage of subjects with a major protocol deviation by type of deviation will be provided. Also, a by-subject listing of major and minor protocol deviations will be provided.

Description	Category	Grade*	Rationale	Comments
Adult < 18 years	Inclusion/Exclusion criteria	Major	Safety	Automatic check
Informed consent form not signed	Inclusion/Exclusion criteria	Major	GCP breach	Automatic check. Patient data could not be used for efficacy assessment
Patient has not histologically confirmed adenocarcinoma of the prostate without neuroendocrine differentiation or small cell features	Inclusion/Exclusion criteria	Major	Efficacy	Manual Review
Patient has not bone metastases due to the prostate cancer and presence of visceral metastases	Inclusion/Exclusion criteria	Major	Efficacy	Manual Review
Serum testosterone of > 1.7 nmol/L (or > 50 ng/dL) at screening	Inclusion/Exclusion criteria	Major	Efficacy Safety	Automatic check
<24 weeks of treatment with abiraterone acetate or enzalutamide within its approved label indication and discontinuation <4 weeks prior to start of study drug at day 1	Inclusion/Exclusion criteria	Major	Efficacy Safety	Manual Review

EudraCT number: 2016-001888-36

Castration-naïve patients treated >six cycles with docetaxel	Inclusion/Exclusion criteria	Major	Efficacy	Manual Review

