No baseline tumor assessment	Inclusion and Exclusion criteria/ Study procedure	Major	Efficacy	If not baseline values any post-baseline data indicating presence of new bone lesions/visceral lesions could be evaluated as evidence of PD Flag if baseline data (CT and bone scans) are >28 days before day 1 cycle 1.

No post-baseline data indicating presence of ≥ 2 new bone lesions or progression as per RECIST 1.1	Study procedure	Major	Efficacy	No evidence of Radiological PD for patients not discontinued due to increased PSA, symptoms or clinical deterioration.
Visits out of window	Study procedure	Minor	Safety	If not performed every 28 days +7 days until EOT; if not performed every 3 months after EOT or if EOS not performed within 3 months after progression, lost to FUP.
Local laboratory tests out of window	Study procedure	Major	Safety	If tests scheduled for day 1 of all cycles (including screening) not performed within 72 hours prior to the dose
Screening assessments out of window	Study procedure	Case by case	Safety	If done >28 days before day 1 cycle 1. Not applicable to local lab tests.
Assessments not done during treatment period (lab value, HRQoL..)	Study procedure	Case by case	Safety	Not applicable to Radiological Assessments. Flag if systematically not done.
Blood sample for translational study not obtained or obtained at incorrect timepoint	Study procedure	Case by case	Efficacy	Depending on which sample is not collected.
Blood sample for translational study obtained out of window at screening	Study procedure	Case by case	Efficacy	Sample not obtained within 72 hours prior to the first dose
Adequate follow-up	Study procedure	Major	Efficacy	If no post-treatment evaluation according to protocol
Prohibited medication was taken	Concomitant medication	Major	Efficacy	If any therapies intended for the treatment of cancer prior to EoT (Cytotoxic chemotherapy, other systemic radioisotopes,

EudraCT number: 2016-001888-36

				radiotherapy, abiraterone acetate, enzalutamide or any antiandrogen)
Prohibited medication was taken	Concomitant medication	On a case by case	Efficacy Safety	If another investigational drug prior to EoT
Subject not withdrawn as per protocol	Administrative and Other	Major	GCP	If data is obtained after withdrawal

\* Major protocol deviation excludes from the full analysis set

\*\* Identification of clinically relevant conditions from the Medical History

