#### 7.1.1 *Primary analysis*

The primary efficacy endpoint is the median PFS achieved with radium-223 treatment. The PFS will be evaluated at the first 34 months period of the study. The PFS will not be evaluated at the 2-years extension of the study for safety.

PFS is a composite endpoint defined as the time from the start of the radium-223 treatment to disease progression in bone or soft-tissue, symptoms, or death, according to the modified PCWG2 criteria.

Objective radiographic disease progression is defined as the presence of at least one of the following conditions:

- Bone lesion progression (appearance of  $\geq$  two new bone lesions compared to baseline).
- Soft-tissue lesion progression according to the RECIST criteria version 1.1.
- Presence of symptomatic skeletal events (pathological fractures, spinal cord compression, radiation or surgery to bone), which should have been reported as adverse event/serious adverse events.

Patients with no progression will be censored at the date of their last evaluation (see Table 1 – Appendix I).

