### **8.5 Handling of missing data**

For time-to-event endpoints, patients without a date of disease progression will be analyzed as censored observations on the date of last tumor assessment. If no post-baseline tumor assessment is available, patients will be censored at the date of first treatment + 1 day. Data for patients with an event (progression) who missed two or more scheduled assessments immediately prior to the event will be censored at the last tumor assessment prior to the missed visits.

For OS, patients who are not reported as having died will be analyzed as censored observations on the date they were last known to be alive. If no post-baseline data are available, OS will be censored at the date of treatment + 1 day.

EudraCT number: 2016-001888-36

For objective response and clinical benefit, patients without any post-baseline assessment will be considered non-responders.

For patients with AR-V7 status not available at baseline, we will assume the AR-V7 status provided at end of treatment or progression, whichever occurs first. Patients with AR-V7 status not available in the study will be considered as AR-V7 negative.

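### A comment in SAP 6.1 lets lesions be read as progression with no baseline scan, contradicting the primary endpoint; whether this reaches the primary result depends on an unresolved full-analysis-set rule

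*SAP*

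**What the plan says.** The SAP 6.1 deviations table has a row for patients with no baseline tumor assessment. It is graded Major, and its comment reads: "If not baseline values any post-baseline data indicating presence of new bone lesions/visceral lesions could be evaluated as evidence of PD".

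The primary endpoint text, SAP 7.1.1 (same wording in protocol 8.3.1), requires at least "two new bone lesions compared to baseline" for bone progression. Protocol 4.2 requires that each "Subject has bone metastases due to the prostate cancer and absence of visceral metastases".

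Four SAP texts bear on whether such a patient is in the primary analysis, which 7.1.1 runs on the full analysis set:

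- Footnote to the 6.1 table: "Major protocol deviation excludes from the full analysis set".
- Body of 6.1: "Patients with major protocol deviations will be excluded from the per protocol set".
- Section 6, definition of the full analysis set: "All patients that accomplish selection criteria and receive at least one dose of study medication".
- Body of 6.1 again: "Criteria for determining full analysis set would be established by the Steering Committee (SC) before the statistical analysis begins".

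For missing scans, SAP 8.5 covers only the opposite case: "If no post-baseline tumor assessment is available, patients will be censored at the date of first treatment + 1 day". Neither 8.5 nor the PFS censoring table in Appendix I has a rule for a missing baseline.

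**The concern.** A lesion is new only by comparison with an earlier image. Without a baseline bone scan, a first on-study scan in a man already known to have bone metastases will be expected to show lesions, and nothing on it separates old from new. The comment nevertheless allows such findings to be treated as evidence of progression. The confirmatory bone scan in protocol 5.2 gives no protection, because old lesions persist as well as new ones.

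The decision would be made at the site: the trial is open-label and SAP 7.1 states that there is no central or independent review. The wording is permissive, so whether a patient has a primary event could turn on discretion.

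At stake are the definition of the primary event and, if these patients are analyzed, some PFS times fixed by the scan calendar rather than by the disease. The first tumor assessment falls at the end of cycle three, so a false event would be dated just below the 3-month null median.

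**Working it through.** **1. Which rule governs the patient?**

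| Text | Consequence for a patient with no baseline scan |
|---|---|
| 6.1 row: graded Major; footnote applied | Out of the full analysis set; no primary event |
| 6.1 body on Major deviations | Out of the per protocol set; full analysis set not mentioned |
| Section 6 definition | In the full analysis set if selection criteria are met and one dose was given |
| 6.1 body on the Steering Committee | Membership criteria still to be set |

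The footnote also clashes with the censoring rules. The 6.1 table grades as Major a patient with no post-baseline tumor assessment, yet 8.5 censors that patient at first treatment + 1 day. It also grades as Major the absence of post-baseline evidence of radiological progression, with a comment limiting this to patients not discontinued for PSA, symptoms or clinical deterioration; yet Appendix I keeps patients without progression and censors them. Both censoring rules presuppose that some patients graded Major remain in the analysis. The documents therefore do not settle the matter.

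**2. The plan's own figure.** Inputs from protocol 8.2: medians 3 and 6.3 months, one-sided alpha 0.05, power 80%, accrual 23 months plus 11 months of follow-up, 25% AR-V7-positive. The test, from SAP 7.1.1, is exponential maximum likelihood.

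- Events = (1.645 + 0.842)² / [ln(6.3/3)]² = 11.23.
- With λ = ln 2/6.3 = 0.110, P(event) = 1 − (e^(−11λ) − e^(−34λ))/(23λ) = 0.892.
- n = 11.23/0.892 = 12.6, so 13 AR-V7-positive patients; 13/0.25 = 52. The stated total is reproduced.

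**3. Effect if the patients stay in and are scored as progressed.** The documents do not say how many patients lack a baseline scan, so k = 0 to 5 of 52 is an assumption. The false event falls at 12 × 7/30.4375 = 2.76 months.

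By expectation, each unaffected patient contributes 0.892 events and 0.892/0.110 = 8.10 months. The estimated median is

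ln 2 × [(52 − k) × 8.10 + k × 2.76] / [(52 − k) × 0.892 + k].

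This gives 6.30 (k = 0), 6.21 (k = 1), 6.02 (k = 3) and 5.83 months (k = 5).

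A simulation (20,000 runs, n = 52, exponential PFS, one-sided 0.05) set each affected patient to an event at the earlier of his own time and 2.76 months:

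| True median (months) | Quantity | k = 0 | k = 1 | k = 3 | k = 5 |
|---|---|---|---|---|---|
| 6.3 | Estimated median | 6.27 | 6.17 | 5.98 | 5.78 |
| 6.3 | Power | 0.999 | 0.999 | 0.999 | 0.997 |
| 4.0 (assumed) | Power | 0.64 | 0.61 | 0.53 | 0.46 |
| 3.0 (null) | Rejection rate | 0.038 | 0.034 | 0.024 | 0.016 |

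At the 6.3-month target the loss is (6.27 − 5.78)/5 ≈ 0.1 month per affected patient.

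**4. Effect if the footnote governs.** With the k patients left out, the estimated median stays at 6.26 to 6.29 months (true 6.3) and 3.97 to 3.99 months (true 4.0). The comment then has no effect on the primary analysis.

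**The case against.** The strongest reply is that the same row cures the problem: it is graded Major, and the footnote takes Major deviations out of the full analysis set. With the body of 6.1, that would leave the patient in neither set used for the primary endpoint. The section 6 definition also requires the selection criteria to be met, and the row's category is partly inclusion and exclusion criteria. This stands as a possible reading, and under it the primary effect is zero. It cannot be relied on, because the footnote conflicts with the texts set out above, and protocol 4.2 and 4.3 do not list baseline imaging as a criterion in its own right.

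A second reply is that the sentence is only a comment. It speaks of new lesions and of what could be evaluated, and may simply explain why the deviation is Major. That is fair, but an ambiguity about what counts as a primary event should be removed before analysis.

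Third, the case should be rare. CT or MRI and a bone scan are mandatory within 28 days before treatment (protocol 5.2), and an older scan is only flagged, so it still serves as a baseline. This stands, and it is why no count is claimed.

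A reader might go further than the documents allow in two ways. The comment gives no lesion count, but silence is not a waiver of the two-lesion threshold, which the next row of the table repeats. The argument about old lesions is also weaker for visceral disease, because visceral metastases are barred at entry; what remains is that their absence is unverified without a baseline CT or MRI.

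**Conclusion.** The contradiction between the 6.1 comment and the primary endpoint definition is real, and no rule covers a missing baseline. Its effect on the primary result is conditional.

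A reader might infer that old metastases will become primary PFS events. The documents do not support that as a certainty: it requires the section 6 definition to prevail over the footnote, and the permissive comment to be used as a scoring rule. A reader might also fear a falsely positive trial, but the bias runs against radium-223.

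If the patients are kept and scored this way, the cost is about 0.1 month of estimated median per affected patient at a true 6.3 months, with power at least 0.997 for up to five patients. A material loss of power appears only if the true median is much nearer the null, as in the assumed 4.0-month case. These sizes rest on exponential PFS, the planned accrual and follow-up, and an assumed number of affected patients. The change is worth making because it concerns the definition of the primary event and is cheap, not because the likely numerical effect is large.

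**What to change.** 1. Delete the sentence on evidence of progression from the 6.1 row.
2. Reconcile the footnote with the full analysis set definition in section 6, the body of 6.1, section 8.5 and Appendix I. State whether patients without a baseline scan are in the full analysis set.
3. If they are, add to 7.1.1 and Appendix I:
   - No scan-based progression is scored for a modality that has no baseline.
   - Death, symptomatic skeletal events, and progression on a modality with a valid baseline still count.
   - A patient without an event is censored at the last assessment of a modality that has a baseline, and at first treatment + 1 day only if no modality has one. This keeps usable follow-up from a patient who lacks just one type of scan.
4. Add a sensitivity analysis of the primary endpoint without these patients.

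The cost is SAP wording and one further analysis. The downside is the loss of a few scan-based events that could not be interpreted.

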- Basic blood test that includes hematological test [hemoglobin, hematocrit, red blood cell count, platelet count, white blood cell count (WBC) with differential count (neutrophils, lymphocytes, monocytes, eosinophils and basophils)], coagulation, chemistry with renal function analysis (serum creatinine, creatinine clearance according to the Cockcroft-Gault formula), liver function [aspartate transaminase (AST), alanine transaminase (ALT), Alkaline phosphatase (AF), gamma-glutamyl transferase (GGT), total and direct bilirubin], glucose, sodium, potassium, calcium, chloride, magnesium, uric acid, total protein, albumin, and lactate dehydrogenase.
- PSA and testosterone determination.
- BPI-SF.
- HRQoL questionnaire (FACT-P, Version 04).
- Blood sample for translational study, which is then sent to central laboratory.
- Assessment of concomitant medications (as it is specified in section 3.3).
- Radiological tumor assessments [torax, abdomen, and pelviscomputerized axial tomography(CT) scan or magnetic resonance imaging (MRI), and bone scan] prior to start first cycle.

Results of standard of tests or examinations available performed as part as clinical practice prior to obtaining informed consent and within 28 days prior to treatment start may be used; such tests do not need to be repeated for screening.

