5.2. Treatment phase: Assessments

All screening assessments must be completed and reviewed to confirm that patients meet all eligibility criteria before treatment starts (day 1). The investigator will maintain a screening log to record details of all patients screened and to confirm eligibility or record reasons for screening failure, as applicable.

Visits are organized in programmed cycles of 28 days (if there are no delays in treatment owing to the occurrence of a side effect). Adjustment of dose level is not permitted. Dose delays are permitted, as described in section 6.11. All visits must occur within \pm 7 working days from the scheduled date, unless otherwise noted in the schedule of assessments. All assessments will be performed on the day of the specific visit unless a time window is specified. Assessments scheduled on the day of study treatment administration should be performed prior to study treatment administration unless otherwise indicated. If a mandatory procedure described in the protocol falls on a bank holiday and/or weekend, this procedure should be performed on the day before or after the holiday (i.e. within a period of \pm 3 working days).

Local laboratory tests scheduled for day 1(before treatment) of all cycles must be performed within 72 hours prior to confirm to the patient if treatment can be followed up. The results of local blood tests should be reviewed, and this review recorded before administration of the study treatment.

Specific study assessments during treatment phase:

During basic safety visits: Day 1of each cycle (every four weeks):

- Assessment of symptoms.
- Physical examination and measurement of weight, vital signs, and ECOG performance status.
- Basic blood test that includes blood count, coagulation, chemistry with renal function analysis (serum creatinine, creatinine clearance according to the Cockcroft-Gault formula), liver function (AST, ALT, AF, GGT, total and direct bilirubin), glucose, sodium, potassium, calcium, chloride, magnesium, uric acid, total protein, albumin, and lactate dehydrogenase.
- PSA determination.
- HRQoL questionnaire (FACT-P, Version 04).
- Assessment of concomitant medications.
- Assessment of AEs.
- Survival.

During full visits: Day 1 of each cycle every three cycles (every 12 weeks):

- Assessment of symptoms.
- Physical examination and measurement of weight, vital signs, and ECOG performance status.

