- Basic blood test that includes blood count, coagulation, chemistry with renal function analysis (serum creatinine, creatinine clearance according to the Cockcroft-Gault formula), liver function (AST, ALT, AF, GGT, total and direct bilirubin), glucose, sodium, potassium, calcium, chloride, magnesium, uric acid, total protein, albumin, and lactate dehydrogenase.
- PSA determination.
- HRQoL questionnaire(FACT-P, Version 04).
- Assessment of concomitant medications.
- Assessment of AEs.
- Tumor assessment: torax, abdomen, and pelvisCT scan or MRI, and bone scan prior to start of cycle every three cycles, every 12 weeks, until progression disease.
- Survival.

Blood assessment schedule for translational study:

- Blood draws prior to the start of study treatment, at the end of treatment and at the time to documented progression disease.

Biological sampling:

The first blood samples should be taken before starting study treatment (see appendix3 for more details on blood sampling procedures). The following samples should be taken at the end of treatment and at the time of disease progression.

At the time of site activation, the Sponsor will provide streck cell-free DNA BCT tubes as well as labels for the storage and transport of samples. No other tubes or labels should be used for this study. If more tubes and labels are required, these should be requested from the Sponsor in writing at least three weeks before they are required (see appendix 3).

Anamnesis and demographic data:

Anamnesis includes clinically significant diseases, surgical interventions, history of cancer (including prior antineoplastic treatments and procedures), history of smoking, alcoholism, drug addiction, as well as any medications (e.g., prescribed drugs, over-the-counter drugs, medicinal plants, homeopathic remedies, or food supplements) used by the patient in the 28 days prior to screening visit. Demographic data will include age, sex, and self-reported race/ethnicity.

Vital signs:

These will include the measurement of height (only during screening), weight, respiratory rate, heart rate, blood pressure, and body temperature. Abnormal or significant changes in vital signs from baseline should be recorded as AEs, if appropriate.

Physical Examination:

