Appendix 1: Schedule of study assessments and procedures

Study Period	Screening	Treatment period		Follow-up period		
Day	-28 to -1	Each cycle* (every 28 days)	End of treatment **	Every 3 months (Efficacy FUP) ¹²	At time of DP**	EoS (Safety FUP) ¹³
Informed Consent ¹	X					
Baseline signs/symptoms	X	X	X	X	X	
Check of inclusion/exclusion criteria	X					
Brief pain inventory (short form) (BPI-SF)	X					
Medical History ²	X					X
Physical Examination and ECOG status ^{3,4}	X	X	X	X	X	

Study Period	Screening	Treatment period		Follow-up period				
Day	-28 to -1	Each cycle* (every 28 days)	End of treatment **	Every 3 months (Efficacy FUP)¹²	At time of DP**	EoS (Safety FUP)¹³		
Concomitant Medication Reporting ⁵	X	X	X	X	X			
Health-related quality of life (HRQoL) questionnaire ⁶	X	X	X	X	X			
AE reporting ⁷	X	X	X	X	X	X		
Radiological Tumor Assessments ⁸	X	every 3 cycles	X	X	X			
Standard Laboratory Procedures								
Hematology ^{9,^}	X	X	X	X	X			
Biochemistry ^{10, ^}	X	X	X	X	X			
PSA determination [^]	X	X	X	X	X			

Study Period	Screening	Treatment period		Follow-up period			
Day	-28 to -1	Each cycle* (every 28 days)	End of treatment **	Every 3 months (Efficacy FUP) ¹²	At time of DP**	EoS (Safety FUP) ¹³	
Testosterone determination [^]	X						
Treatment Administration							
Radium-223 at dose of 55 kBq/Kg one IV injection		D1 (for a total of six IV injections)					
Research Central Laboratory Procedures							
Blood sample collection (split variant AR-V7 determination) ¹¹	X		X		X		
Blood sample collection (CTC count) ¹¹	X		X		X		

-
- * All visits must occur within \pm 7 working days from the scheduled date.
 - ** If disease progression coincides with the end of treatment visit, the evaluations planned for both visits will coincide, they will only be performed once (including blood sample for central laboratory).

 - ^ Local laboratory tests scheduled for day 1 of all cycles must be performed within 72 hours prior to confirm to the patient if treatment can be followed up.
 - 1. Signed written informed consent obtained prior to any trial-specific procedure.
 - 2. Complete medical history and demographics (including age, gender, and ethnic origin) and all medications taken the last 28 days prior to enrollment will be collected.
 - 3. Physical examination and vital signs (including respiratory rate, blood pressure measurements, heart rate, and body temperature) and weight measurement will be performed prior to enrollment.

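### SAP 6.1 holds screening laboratory tests to a 72-hour window and pre-grades a breach Major, although the protocol allows 28 days, so some protocol-compliant patients are marked for exclusion from the per protocol set

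*SAP*

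**What the plan says.** **Protocol.** Section 5.1 lists haematology, biochemistry, PSA and testosterone among the screening procedures. It accepts results from routine practice obtained before consent: those "within 28 days prior to treatment start may be used; such tests do not need to be repeated for screening". The screening column of Appendix 1 runs from day -28 to day -1. Section 5.2 has a separate rule for treatment visits: "Local laboratory tests scheduled for day 1(before treatment) of all cycles must be performed within 72 hours prior to confirm". The Appendix 1 footnote on the laboratory rows repeats it: "Local laboratory tests scheduled for day 1 of all cycles must be performed within 72 hours prior to confirm to the patient". Neither statement names screening.

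**SAP 6.1, deviation table.** Local laboratory tests out of window are graded Major, with the comment "If tests scheduled for day 1 of all cycles (including screening) not performed within 72 hours prior to the dose". The next row, screening assessments out of window, is graded case by case, with the comment "If done >28 days before day 1 cycle 1. Not applicable to local lab tests".

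**Consequence of a Major grade.** The per protocol set definition in SAP 6 and the text of SAP 6.1 exclude patients with major deviations from the per protocol set. The footnote to the 6.1 table says instead that a Major deviation excludes from the full analysis set. SAP 6.1 also provides for all deviations to be reviewed before database lock to decide which are major. SAP 7.1.1 makes the full analysis set primary and the per protocol set supportive. SAP 7.2 bases secondary analyses on both sets.

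**The concern.** The two SAP rows act together. One brings screening laboratory tests under the 72-hour rule, and the other takes them out of the 28-day rule. No row then applies the window that the protocol gives to sites. A screening assessment other than a laboratory test that is done too early, in real breach of the protocol, is judged case by case. A screening laboratory test done on a permitted day is pre-graded Major.

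Membership of the per protocol set would then depend partly on how a site arranged its screening visits, not on any departure from the protocol. A per protocol analysis is meant to show the result in patients treated as planned, and exclusions of this kind blur that. If the grade is left to be corrected at the pre-lock review, set membership becomes a matter of discretion in an open-label, single-arm trial.

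**Working it through.** The point rests on comparing texts. The arithmetic only shows scale.

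**Step 1. Windows side by side**

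| Test | Protocol | SAP 6.1 table |
|---|---|---|
| Screening laboratory tests | Up to 28 days before treatment (5.1; Appendix 1, days -28 to -1) | 72 hours before the dose, Major; 28-day row switched off |
| Day 1 laboratory tests, all cycles | 72 hours (5.2; Appendix 1 footnote) | 72 hours, Major |
| Other screening assessments | Up to 28 days before treatment | 28 days, case by case |

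Only the first line disagrees.

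**Step 2. Who is wrongly flagged.** 72 hours is 3 days, so screening samples from day -28 to day -4 fall outside the SAP window.

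- Screening tests at day -28 to -4, plus a cycle 1 day 1 test within 72 hours: compliant with the protocol, Major under the SAP. This is the wrongly flagged group.
- Screening tests at day -28 to -4, and no later test before the first dose: already in breach of Protocol 5.2, which covers cycle 1. Not wrongly flagged.
- Screening tests within 72 hours of the dose: compliant under both.

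**Step 3. Planned sample size, for context.** Inputs from Protocol 8.2: median PFS 3 against 6.3 months, one-sided alpha 0.05, power 80%, accrual 23 months, follow-up 11 months, 25% AR-V7-positive. Exponential survival is assumed.

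- Events = (1.645 + 0.842)² / [ln(6.3/3)]² = 11.23.
- With λ = ln 2 / 6.3, A = 23 and F = 11: P(event) = 1 - [exp(-λF) - exp(-λ(A+F))] / (λA) = 0.892.
- n = 11.23 / 0.892 = 12.6, rounded up to 13 AR-V7-positive patients; 13 / 0.25 = 52.

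This reproduces the plan's 52, which is not in dispute.

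**Step 4. Illustrative shrinkage.** The documents give no laboratory dates, so the flagged share f is an assumption. Remaining n = 52 × (1 - f). Approximate total-sample power = Φ(√(0.892 n) × ln(6.3/3) - 1.645), treating exclusion as unrelated to outcome.

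| f (assumed) | Remaining | Power |
|---|---|---|
| 0% | 52 | above 99.9% |
| 10% | 46.8, about 47 | 99.9% |
| 25% | 39 | 99.7% |
| 50% | 26 | 97.3% |

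The total sample keeps its power across this range. The damage is to what the per protocol set means and to its size, not to the primary test.

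**The case against.** The strongest reply is that the SAP sentence is about tests scheduled for day 1, so the mention of screening may mean only the pre-dose sample of cycle 1, which the protocol already holds to 72 hours. The Appendix 1 footnote marker lends some support: it also sits on the testosterone row, which is marked only at screening. This explains how the SAP wording may have arisen, but it does not rescue it. Cycle 1 is already included in all cycles, so the added words would do nothing, and this reading does not explain why the next row exempts local laboratory tests from the 28-day limit. If it was the intention, the row still needs rewording, because a programmed check would flag compliant samples.

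Three other replies stand and limit the point:

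- Exclusion is not automatic. SAP 6.1 has a pre-lock review, and SAP 6 leaves the per protocol criteria to the Steering Committee. The table nevertheless pre-grades this row Major while many other rows are case by case.
- The per protocol result is supportive only. A reader might infer that the per protocol set alone carries the secondary analyses, but SAP 7.2 uses both sets and SAP 7.1 bases all efficacy analyses on the full analysis set.
- A reader might infer that a testosterone flag could never be cleared by a later sample. The documents do not settle this. Appendix 1 marks testosterone at screening only, but the laboratory paragraph of Protocol 5.2 lists it among tests before treatment administration, and SAP 8.4.4 summarises it by time point.

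**Conclusion.** The SAP contradicts the protocol on the window for screening laboratory tests. Followed as written, it pre-grades as Major those compliant patients who had screening tests earlier than 72 hours before dosing and a timely cycle 1 day 1 test. They leave the per protocol set unless the pre-lock review intervenes. If the table footnote were followed instead of the text of SAP 6.1, they would also leave the full analysis set, which carries the primary analysis. The footnote and the text conflict and must be reconciled.

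The number affected cannot be derived from the documents. The figures of about 47, 39 or 26 remaining are illustrations at assumed shares of 10%, 25% and 50%. Since 25 of the 28 permitted days lie outside 72 hours, a reader might infer that nearly all compliant patients would be flagged. That would require screening dates spread evenly over the window, which nothing in the documents supports.

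A reader might also extend the point to the baseline AR-V7/CTC sample, for which the SAP comment is "Sample not obtained within 72 hours prior to the first dose" while Protocol 5.2 asks for "Blood draws prior to the start of study treatment, at the end of treatment and at the time to documented progression disease". The texts do differ, but this does not establish wrongful exclusion. The row is case by case, and the molecular analyses use the modified full analysis set, whose definition does not refer to major deviations. The protocol is also not uniform on timing: 3.2 describes the baseline sample under the treatment phase, once the screening criteria are met, while 5.1 and Appendix 1 place it in screening.

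**What to change.** 1. In the local laboratory row of the SAP 6.1 table, delete the parenthesis that adds screening, so that 72 hours applies only to day 1 tests of each cycle, cycle 1 included.
2. In the screening assessments row, delete the sentence exempting local laboratory tests, so that the protocol's 28-day window governs screening laboratory tests, including testosterone where it is drawn only at screening.
3. Reconcile the table footnote with the text of SAP 6.1 and the set definitions in SAP 6, so that one statement says which analysis set a Major deviation affects.
4. For the translational sample, only reconcile the SAP's 72-hour window with Protocol 3.2, 5.1, 5.2 and Appendix 1.

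The first two edits cure the main point. They cost two wording changes and an update to the programmed checks, made before database lock. No new data are needed.
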